Subjects will be monitored for safety, tolerability, immunogenicity, PK, and TG2 levels for 84 days post-dose and will attend ambulatory visits on Days 2, 5, 7, 14, 28, 56, and 84 (end of study). The total duration of participation is expected to last approximately 16 weeks. The end of the study is defined as the last visit of the last subject in the study. Even if not mandatory, overnight stay is always possible for logistical reasons or to accomplish site/subject preferences.

An overview of the study design is shown in Figure 1.

Figure 1: Study Design

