7.2.2.4 Immunogenicity

The following blood samples will be collected pre-dose and Days 14, 28, 56, and 84:

- 5 mL of blood for immunogenicity assessments (serum non-isotype ADAs) and nAb (in case of ADA positive result).

The analytical procedures will be described in a separate analytical protocol. Validation data and details of the analytical procedures will be gathered in an analytical report that will be included in the Clinical Study Report. The processing, storage and shipment of samples are detailed in the Laboratory Manual document.

Antibodies to CHF10067 will be evaluated in blood samples collected from all subjects according to the study schedule (Section 7.1). Additionally, samples should be collected at the early termination visit from subjects who discontinued study drug or were withdrawn from the study. These samples will be tested by the Sponsor or Sponsor's designee.

Clinical Study Code No.: CLI-10067AA1-01	Version No.: 6.0
EUDRACT No.: 2022-001079-15	Date: 06 July 2023

Samples will be screened for antibodies binding to CHF10067, and the titer of confirmed positive samples will be reported. Other analyses may be performed to further characterise the immunogenicity of CHF10067. In particular, positive ADA samples will be also evaluated for the presence of IgE CHF10067, to clarify the relationships between this ADA subtype and the presence of adverse reactions.

The detection and characterisation of antibodies to CHF10067 will be performed using a validated assay method by or under the supervision of the Sponsor. All samples collected for detection of antibodies to study drug will also be evaluated for CHF10067 concentration, to enable interpretation of the antibody data. Antibodies may be further characterised and/or evaluated for their ability to neutralise the activity of the study drug. Samples may be stored for a maximum of 20 years (or according to local regulations) following the last subject's final visit for the study at a facility selected by the Sponsor to enable further analysis of immune responses to CHF10067.

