2.2 IMMUNOGENICITY

2.2.1 *Available data*

Serum samples for anti-drug antibody (ADA) assessments will be conducted utilizing a tiered approach (i.e., screen, confirm, titer), and ADA data will be collected pre-dose and at Days 14, 28, 56, and 84 and in case of early termination visit.

[figure not shown]
ADA result from each sample will be reported as either:

- ADA-positive: when ADA is detected at both screening and confirmatory tests in a sample, the sample is considered positive.
- ADA-negative: when ADA is not detected at screening test OR ADA is detected at screening but not detected at confirmatory test, the sample is considered negative.
- ADA-unevaluable: when a sample could not be tested for ADA status (“un-assayed sample”) due to inadequate sample volume, mishandling, or errors in sample collection, processing, storage, etc., either at screening or confirmatory test.

If the confirmatory sample is positive (i.e., ADA-positive sample), the ADA titer will be reported as well. ADA titer is a quasi-quantitative expression of the level of ADA in the sample.

In addition, the presence of neutralizing antibody (nAb) will be tested for all ADA -positive samples using a ligand-binding assay. The nAb results will be reported as either positive or negative.

ADA sample results

2.2.2 *Derivation rules*

No data imputation will be performed for missing and/or unevaluable samples.

Using the sample ADA status, subjects will be classified using the following definitions:

- **ADA evaluable subject**: A subject with baseline sample and at least one sample taken after drug administration during the treatment periods that are appropriate for ADA testing (i.e., with reportable result).
- **ADA unevaluable subject**: A subject without an evaluable sample at baseline OR with reportable baseline result but without a single sample taken (or without a reportable result) after drug administration during the treatment period.
- **ADA-positive subject (ADA+)**: A subject with at least one treatment-induced or treatment-boosted ADA-positive sample at any time during the treatment period. See definitions of treatment-induced and treatment-boosted ADA in Section 2.2.3.
- **ADA-negative subject (ADA-)**: A subject without a treatment-induced or treatment-boosted ADA-positive sample during the treatment period.

2.2.3 *Presentation of results*

The number and percentage of subjects who fulfil the below criteria will be presented by treatment.

- **Baseline ADA-positive**

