10. APPENDICES

10.1 SAS CODE

The SAS code in this section is an example and might differ from the actual code used in the statistical analysis.

Dose proportionality on CHF10067 serum PK parameters:

```
proc mixed data=dataset;
  by param;
  model logPK = logDOSE;
  estimate 'slope' logDOSE 1 / cl alpha = 0.1;
  ods output estimates = diff;
run;
```

Notes:

- Dataset: analysis dataset of PK parameters. One record per subject per parameter;
- Param (character): PK parameter name and/or identifier;
- LogPK (numeric): log value of PK parameter;
- LogDOSE (numeric): log value of doses (1000mg; 2000mg; 3000mg).

Statistical Analysis Plan

CLI-10067AA1-01

Final Analysis

Final 1.0 of 30MAY2024

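### The SAP counts an ADA non-detect as negative whatever the CHF10067 level in the sample, so by-dose immunogenicity can be understated if residual drug exceeds the assay's tolerance

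*SAP*

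**What the plan says.** **Sample level (SAP 2.2.1).** A sample is positive if both the screening and the confirmatory tests detect ADA. It is negative "when ADA is not detected at screening test OR ADA is detected at screening but not detected at confirmatory test". The only other class, unevaluable, applies "when a sample could not be tested for ADA status", for reasons such as low volume or mishandling. Interference by drug is not named.

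**Subject level (SAP 2.2.2).** A subject is evaluable with a reportable baseline result and at least one reportable result after dosing. An ADA-negative subject is "A subject without a treatment-induced or treatment-boosted ADA-positive sample during the treatment period". No sample with a low drug level is required.

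**Drug measurement (Protocol 7.2.2.4).** "All samples collected for detection of antibodies to study drug will also be evaluated for CHF10067 concentration, to enable interpretation of the antibody data". SAP 2.2.1 to 2.2.3 do not refer to this measurement. SAP 7.1 explains the rewritten immunogenicity section but does not mention it either.

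**Timing.** SAP 2.2.1 states that "ADA data will be collected pre-dose and at Days 14, 28, 56, and 84", plus early termination. Protocol 3 fixes the same follow-up for all cohorts: "Subjects will be monitored for safety, tolerability, immunogenicity, PK, and TG2 levels for 84 days post-dose".

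**Displays.** Table 14.2.4.1 gives ADA responses by treatment. Listing 16.2.6.1 is described as covering ADA-positive subjects, and the drug concentration in the ADA sample is not among its stated items.

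**The concern.** Drug circulating in a sample can bind antibody and hide it from a binding assay. A non-detect with much drug present is then not evidence that antibody is absent. The protocol's reason for measuring drug in each ADA sample implies that the two results should be read together, but the SAP's rules read the ADA result alone.

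If masking occurs, several outputs inherit it:

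- **Incidence by dose** counts an uninterpretable non-detect as a true negative, more often where more drug remains.
- **Time to onset** is dated from the first readable positive, which may come well after the antibody appeared.
- **Persistence** (SAP 2.2.3) needs two non-consecutive positive time points, the last at Day 84 for completers. With samples on Days 14, 28, 56 and 84, that means a positive by Day 28 as well as at Day 84. A subject masked through Day 28 can only be called transient.
- **nAb** is tested only in ADA-positive samples, so a masked sample never reaches that test.
- **PK curves by ADA status.** Within a dose, subjects with higher exposure would be more likely to be labelled ADA-negative. Lower exposure among positives could then arise partly from the labelling.

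Immunogenicity is a secondary objective, and Protocol 1.2 says these data will help establish doses for future studies.

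**Working it through.** The plan states no figure for this point, so there is none to reproduce.

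**Inputs from the documents**
- Doses of 1000, 2000 and 3000 mg, with 6 active subjects at each (SAP 1.2).
- Post-dose ADA samples on Days 14, 28, 56 and 84. SAP 6.2.4 sets the Day 84 target for PK at 1992 h, and 1992/24 = 83 days. The same count gives 13, 27, 55 and 83 days.

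**Assumptions, not in the documents**
- Half-life h of 7, 14, 21 or 28 days.
- Single-exponential decline and dose-proportional concentrations.
- Assay tolerance T, expressed as a percentage of the starting concentration at 1000 mg.

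**Step 1: delay between doses.** With concentration proportional to dose × 0.5^(t/h), the time to fall to a fixed level differs between 3000 and 1000 mg by h × log2(3) = 1.585h.

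**Step 2: drug left on Day 84**, as a percentage of the 1000 mg starting concentration. At 1000 mg this is 100 × 0.5^(83/h); the other doses are 2 and 3 times that.

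| h (days) | Delay 1.585h (days) | 1000 mg | 2000 mg | 3000 mg |
|---|---|---|---|---|
| 7 | 11.1 | 0.03 | 0.05 | 0.08 |
| 14 | 22.2 | 1.6 | 3.3 | 4.9 |
| 21 | 33.3 | 6.5 | 12.9 | 19.4 |
| 28 | 44.4 | 12.8 | 25.6 | 38.4 |

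**Step 3: when Day 84 differs by dose.** A sample is readable if its drug level is at or below T. There are three cases:
- T at or above the 3000 mg value: Day 84 is readable at every dose.
- T below the 1000 mg value: Day 84 is readable at none.
- T between them, a 3-fold band: Day 84 is readable at 1000 mg but not at 3000 mg, and equal true immunogenicity can look lower at 3000 mg.

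**Step 4: readable post-dose samples out of 4, at 1000/2000/3000 mg**
- h = 14, T = 3%: 1/0/0.
- h = 21, T = 10%: 1/0/0.
- h = 28, T = 20%: 1/0/0.
- h = 7, T = 0.5%: 2/1/1. Day 84 is readable at all doses. Day 56 is readable only at 1000 mg (0.43%, against 0.86% and 1.29%), so onset can still be affected.

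**Step 5: can the counts reveal masking?** With 0 of 6 positive, the exact 95% upper limit is 1 − 0.025^(1/6) = 46%. Zero of 6 arises by chance with probability 0.8^6 = 26% at a true rate of 20%, and 0.7^6 = 12% at 30%. A low count at one dose cannot separate masking from chance.

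**The case against.** A reader might infer that incidence will be understated at 3000 mg, or that the dose ordering is biased. The documents do not support that. They give neither half-life nor assay tolerance, and the assay procedures sit in a separate analytical protocol. Linear kinetics is itself something the SAP examines. At Day 84 the 1000 versus 3000 mg comparison is distorted only inside the 3-fold band. One induced or boosted positive at any visit makes a subject ADA-positive, so a late readable sample can recover a lasting response. The diagram of ADA sample results in SAP 2.2.1 could not be read here, so an extra branch in it cannot be ruled out, though the text describes none.

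A reader might also infer that the SAP contradicts the protocol. It does not: the protocol measures drug to help interpretation and prescribes no reclassification.

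Much of the raw material is already displayed. PK samples fall on the same days as ADA samples. Table 14.2.2.2 and Listing 16.2.5.2 show individual concentrations. Figure 16.2.5.1 plots each subject's curve, coloured by ADA status. SAP 2.2.3 promises that all immunogenicity data will be listed, and validation data go into the Clinical Study Report. The mean PK curves and safety table by ADA status are produced only with at least 3 ADA-positive subjects. No test of ADA between doses is planned, and 6 subjects per dose is weak evidence in any case.

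These points limit the strength of the concern but do not remove it. None of these displays shows a tolerance limit or marks a negative as uninterpretable, and the figures apply the same unqualified negative label. The stated rule still counts such a sample as a true negative in the incidence table.

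**Conclusion.** The gap in the rules is certain; its effect is conditional. SAP 2.2.1 and 2.2.2 define negative samples and subjects without regard to drug level, although the protocol collects that level to interpret them. If drug exceeds the assay's tolerance at the sampling times, masking can last longer at higher doses: 11 to 44 days longer at 3000 than at 1000 mg, for assumed half-lives of 7 to 28 days under linear kinetics. Incidence can then be understated, onset delayed and persistence misclassified, most at the top dose.

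The size cannot be fixed from the documents. If the assay tolerates the Day 84 level at 3000 mg, there is no Day 84 effect and only earlier samples are in question. The matter deserves a defined rule because counts from 6 subjects per dose could not expose the problem afterwards.

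**What to change.** - **SAP 2.2.1:** cite the drug tolerance from assay validation, fixed before results are disclosed. Add a class ADA-inconclusive for a non-detect with CHF10067 above that limit, using the concentration in the ADA sample itself. This also covers early termination, where the schedule has an ADA sample but no PK sample.
- **SAP 2.2.2:** call a subject ADA-negative only if there is no treatment-induced or treatment-boosted positive and at least one post-dose negative, preferably the last, is at or below tolerance. Otherwise class a subject without such a positive as inconclusive.
- **Table 14.2.4.1:** give incidence over all ADA-evaluable subjects as the main figure. Add the number of inconclusive subjects by dose and of negative samples above tolerance by visit. Give bounds with inconclusive subjects counted as all negative and as all positive.
- **Do not report incidence among conclusive subjects only.** It keeps positives at any drug level but drops high-drug negatives, and so pushes incidence up at the top dose. With 1 positive and 5 inconclusive of 6, it gives 1/1 = 100%; the bounds give 1/6 = 17% to 6/6 = 100%.
- **Listing:** show the CHF10067 concentration beside every ADA result for all subjects, not only ADA-positive ones.
- **Other displays:** carry the third class into Table 14.2.4.2, Figures 14.2.4.1 and 16.2.5.1, and TG2 Figure 16.2.11.1.

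The cost is SAP wording and small edits to several displays. No new samples are needed, because the concentrations are already planned. Fewer subjects may be called negative. If tolerance is never exceeded, the new rows show zeros and the negatives become more credible.

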For this group of subjects, titer range (median and interquartile range (IQR)) of the baseline ADA-positive samples will be reported.
- **ADA positive at any visit (ADA prevalence)**
A subject with at least one positive ADA result available at any time, including baseline (i.e., pre-existing ADA) and post-baseline measurements (i.e., ADA+). For this group of subjects, peak positive titer and range (median, IQR) will be reported.
- **ADA incidence**
 - **Treatment-induced ADA**, defined as ADA developed de novo (seroconversion) following drug administration (i.e., formation of positive ADA any time after the drug administration in subjects with ADA-negative baseline).
For this group of subjects, the following additional parameters will be presented:
 - Peak positive titer and range (median, IQR);
 - **Onset of ADA**
Time to onset of ADA (i.e., time period between the initial administration of the drug and the first instance of treatment-induced ADA);
 - **Duration of ADA**
 - **Persistently positive ADA**
Subjects having a treatment-induced ADA detected at

least two non-consecutive time points, with the last ADA-positive measurement (irrespective of any negative samples in between first and last positive measurements) being detected at the end of the study period (i.e., day 84) for completer subjects or at the last available sampling time point for prematurely discontinued subjects.

- *Transiently positive ADA*

Subjects having a treatment-induced ADA not fulfilling the above condition for persistently positive.

- Treatment-boosted ADA, defined as a baseline positive ADA titer (i.e., pre-existing ADA) that was boosted to a 4-fold or higher level following drug administration.

For this group of subjects, the fold increase in titer (ratio of peak post-administration titer to baseline titer) and range of titer increases (median, IQR) will be presented.

The combination of both treatment-induced and treatment-boosted ADA (i.e., the percentage of patients fulfilling this criterion) is defined as ADA incidence.

- nAb positive at any visit (including baseline and all post-baseline measurements).

All immunogenicity data will be listed.

Only if immunogenicity data will allow (i.e., if the number of ADA+ subjects will be ≥ 3), the effect of immunogenicity on PK and safety will be evaluated:

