7. CHANGES TO THE PLANNED ANALYSIS

7.1 CHANGES NOT COVERED BY PROTOCOL AMENDMENTS BEFORE UNBLINDING

- **“Immunogenicity Analysis”:** Section 2.2 of the SAP to clarify section ‘12.3.5.3 Immunogenicity’ of the study protocol.
Section 2.2 of this SAP, compared to Section 12.3.5.3 of the study protocol, provides clear definitions and a corresponding summary table on the whole Safety Set for: ADA evaluable subject, ADA positive subjects, ADA prevalence, ADA incidence (i.e., treatment-induced and treatment-boosted ADA) and nAb positive subject. As a consequence of the above update, the two summary tables on the subset of ADA positive subjects, initially foreseen in Section 12.3.5.3 of the study protocol, have been translated into a listing (see Listing 16.2.6.1 at Section 9.2 of the present document).
- **“Vital signs”:** Section 3.3 of the SAP to clarify section ‘12.3.5.4.3 Oxygen saturation’ of the study protocol.
While per protocol, individual time profile plots are not requested for oxygen saturation, these will be produced to be in line with the vital signs analysis.
- **“Lung function”:** Section 3.5 of the SAP to clarify section ‘12.3.5.4 Pulmonary assessments’ of the study protocol.
The following summary analysis is described in the protocol:

“The frequency of subjects with FEV1% and FVC% below the lower limit of normal at each timepoint will be listed and summarised with descriptive statistics.”

Since no normal ranges are available for the aforementioned parameters, this summary will not be produced.

- **“Placebo-corrected change from baseline”:** Section 3.4 of SAP to clarify Section ‘12.3.5.5 ECG’ of the study protocol.
Placebo-corrected change from baseline is erroneously mentioned in the protocol but it is not applicable for this study design. Therefore, none of the analyses related to placebo-related change from baseline will be produced.

	Statistical Analysis Plan	
CLI-10067AA1-01	Final Analysis	Final 1.0 of 30MAY2024

- **Section “12.3.6.1 TG2 in plasma” of the study protocol.**

The below text was erroneously included in the study protocol.
Therefore, the related analyses will not be produced.

“The TG2 levels in plasma obtained from healthy subjects will be summarised using descriptive statistics.

Box-plots summarising the pre-dose levels for treated subjects in the study, the healthy subjects’ external group, and each post-dose levels for the different doses for treated subjects will be presented.”

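### Read literally, the SAP's ADA-negative definition takes in every ADA-unevaluable subject, including one with no baseline result who is antibody-positive after dosing

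*SAP*

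**What the plan says.** SAP 2.2.2 gives four subject-level definitions in one list.

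- Evaluable: a reportable baseline result and at least one reportable post-dose result.
- Unevaluable: "A subject without an evaluable sample at baseline OR with reportable baseline result but without a single sample taken" (or without a reportable result) after dosing.
- ADA-positive: "A subject with at least one treatment-induced or treatment-boosted ADA-positive sample at any time during the treatment period".
- ADA-negative: "A subject without a treatment-induced or treatment-boosted ADA-positive sample during the treatment period".

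The same section states "No data imputation will be performed for missing and/or unevaluable samples".

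SAP 2.2.3 supplies the two terms on which the last two definitions rest. Treatment-induced ADA is "formation of positive ADA any time after the drug administration in subjects with ADA-negative baseline". Treatment-boosted ADA is "defined as a baseline positive ADA titer (i.e., pre-existing ADA) that was boosted to a 4-fold or higher level following drug administration". Incidence is then set out separately: "The combination of both treatment-induced and treatment-boosted ADA (i.e., the percentage of patients fulfilling this criterion) is defined as ADA incidence". SAP 7.1 says that the new immunogenicity section "provides clear definitions and a corresponding summary table on the whole Safety Set".

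**The concern.** The list has an unevaluable class, but nothing says that ADA-positive and ADA-negative apply only to evaluable subjects, or that the classes exclude one another. ADA-negative is worded as the plain complement of ADA-positive, so anyone who cannot be shown to be positive falls into it by default.

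Immunogenicity is a secondary objective, and ADA status is carried into other displays as a two-level variable. It sets the colours in the individual PK plots (SAP 2.1.4) and the individual TG2 plots (SAP 4.1.2), and both sections point back to the definitions in 2.2.2. It also splits the PK mean curves and the TEAE summary (end of SAP 2.2.3). With 6 active subjects per dose, one subject under the wrong label can visibly change an ADA-negative mean curve or TEAE column.

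The situation is foreseeable. Only one pre-dose ADA sample is scheduled, so one lost or unassayable tube can remove the baseline. The first scheduled post-dose ADA sample is on Day 14, and Protocol 4.4 provides for subjects who discontinue before then. An early-termination ADA sample is planned (Protocol 7.1.3), but only if consent has not been withdrawn and the visit takes place. A dosed subject remains in the Safety Set in either case.

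**Working it through.** The documents give no expected ADA rate and no expected number of unevaluable subjects, so there is no planned figure to reproduce. The check has two parts.

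**1. Literal classification.** Each baseline and post-dose pattern is put through the wording of SAP 2.2.2 and 2.2.3.

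| Baseline | Post-dose | Evaluable | ADA+ | Literally ADA- | Counts in prevalence |
|---|---|---|---|---|---|
| negative | any positive | yes | yes | no | yes |
| negative | all negative | yes | no | yes | no |
| positive | rise of 4-fold or more | yes | yes | no | yes |
| positive | 2-fold rise | yes | no | yes | yes |
| none | positive | no | no | **yes** | yes |
| none | negative | no | no | **yes** | no |
| negative | none | no | no | **yes** | no |
| positive | none | no | no | **yes** | yes |

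All four unevaluable patterns are also ADA-negative. In the fifth row, induced ADA fails because there is no negative baseline, and boosted ADA fails because there is no baseline titre. With no imputation, the gap stays. The prevalence item in 2.2.3 adds to the ambiguity: a parenthesis there equates positive post-baseline measurements with ADA+, so two programmers could code this subject in opposite ways.

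**2. Effect on incidence.** Let n be the Safety Set subjects in the group, u the unevaluable subjects and x the subjects with induced or boosted ADA. The numerator x is counted directly from the induced and boosted definitions and does not use the ADA-negative definition. Only the denominator can matter:

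- all Safety Set subjects: x/n
- ADA-evaluable subjects only: x/(n - u)

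From SAP 1.2, n = 6 active subjects per dose, and 3 × 6 = 18 for CHF10067 Total. The values of x and u are assumptions.

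| n | u | x | x/n | x/(n - u) | Difference (points) |
|---|---|---|---|---|---|
| 6 | 1 | 0 | 0.0% | 0.0% | 0.0 |
| 6 | 1 | 1 | 1/6 = 16.7% | 1/5 = 20.0% | 3.3 |
| 6 | 1 | 2 | 2/6 = 33.3% | 2/5 = 40.0% | 6.7 |
| 6 | 1 | 3 | 3/6 = 50.0% | 3/5 = 60.0% | 10.0 |
| 6 | 2 | 2 | 2/6 = 33.3% | 2/4 = 50.0% | 16.7 |
| 18 | 1 | 3 | 3/18 = 16.7% | 3/17 = 17.6% | 1.0 |
| 18 | 2 | 3 | 3/18 = 16.7% | 3/16 = 18.8% | 2.1 |

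The SAP does not say which column applies. Section 6.4.1 has two rules: event-type data are divided by all subjects in the analysis set, while frequency tabulations leave out missing values. Neither is assigned to ADA. Under the second rule, dilution would still occur if the literal ADA-negative label made the status non-missing; it would not occur if unevaluable status were treated as missing.

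**The case against.** The strongest reply is that the intent is clear enough. Unevaluable is a class of its own in the same list, and calling a subject with no result negative sits badly with the no-imputation rule. SAP 7.1 includes the evaluable count among the items in the summary table. A no-baseline positive is still counted in ADA prevalence and, if neutralising, in nAb positive at any visit; 2.2.3 also says that all immunogenicity data will be listed. The PK mean curves and TEAE split are produced only with at least 3 ADA-positive subjects. ADA is sampled at four post-dose visits and at early termination, so a subject with no post-dose result must have missed them all. At this sample size the percentages are descriptive: exact 95% intervals are about 4% to 78% for 2/6 and 5% to 85% for 2/5.

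Much of this stands. It limits the consequences but does not remove the overlap. The intended hierarchy is an inference, because no sentence states it. The summary items in 2.2.3, which Table 14.2.4.1 follows, include no evaluable or unevaluable row. The promise to list all data is weakened by SAP 9.2, where the only immunogenicity listing (16.2.6.1) is described as covering ADA-positive subjects.

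A reader might go further and infer that ADA incidence is understated. The documents do not support that as a general statement. The incidence numerator does not depend on the ADA-negative wording, and rewording that definition alone would leave it unchanged. The Safety Set reference in 7.1 names the population of the table, in contrast to the protocol's tables on ADA-positive subjects only; it does not fix the divisor of each percentage. Nor is the no-baseline subject a known treatment-emergent positive called negative. Without a baseline, pre-existing antibody cannot be told apart from antibody formed after dosing, so the true group is unknown.

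**Conclusion.** The point holds as a classification error in the stated rule. Under the literal wording, every ADA-unevaluable subject is also ADA-negative, including one with no baseline who is antibody-positive after dosing, and no other section removes the overlap.

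The effect on the individual PK and TG2 plots needs only one unevaluable subject in the display. The effect on the PK mean curves and TEAE table needs, in addition, at least 3 ADA-positive subjects.

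For incidence, the supportable statement is that the denominator is not named. Dilution needs three things together: a denominator of all Safety Set subjects, at least one unevaluable subject, and at least one positive in the group. With one unevaluable subject among 6 and 0 to 3 positives, all assumed, the difference is 0 to 10.0 percentage points; for CHF10067 Total with 3 positives it is 1.0 point. The SAP should be changed because the remedy is nearly free and each dose group is small, although no primary conclusion depends on it.

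**What to change.** Amend SAP 2.2.2 and 2.2.3 before the blind is broken, along these lines:

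> ADA+ and ADA- are assigned to ADA-evaluable subjects only. All other Safety Set subjects are ADA-unevaluable. The denominator for ADA incidence is the number of ADA-evaluable subjects who received that treatment. A subject with a positive post-dose sample and no baseline result is ADA-unevaluable, counts in prevalence, and is footnoted and listed.

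Then:

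- show ADA-unevaluable as a third category in Table 14.2.4.1, the individual PK and TG2 plots, the PK mean curves and the TEAE table by ADA status;
- align the parenthesis in the prevalence item of 2.2.3 with the ADA+ definition;
- extend Listing 16.2.6.1, or add a listing, so that post-dose positives without a baseline appear.

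The cost is SAP wording, one extra table row or category, and a listing condition. Data collection does not change.
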